3.7.5.2 Criteria for “harmful”

We will consider the digital interventions (MEL-T01 or MEL-S01) to be harmful if TAU is superior to either intervention so that:

The reduction in PHQ-9 score from T0 to T3 is

greater for TAU than for MEL-T01

OR

greater for TAU than for MEL-S01.

If either of the superiority conditions are met in a one-tailed t-test (or in a one-tailed Wilcoxon test if the conditions defined in [3.7.3](#) for using a parametric test are not met) with a Bonferroni-corrected ($N_{\text{tests}} = 2$) alpha-level of 0.0125, we consider the digital intervention as harmful to the subjects and terminate the investigation immediately.

Here, it is important to note that, at the discretion of the investigators, it is also possible to halt or terminate the investigation on the basis of harmfulness also at times other than that of the Interim analysis. As described in [3.15.2.2](#), evidence for such harmfulness could be excessive AEs in many subjects or an SAE that is related to the investigational device and may potentially be experienced by other than the subject first reporting it.

3.7.5.3 Criteria for “futile”

The study may be considered futile, if it becomes clear that the subjects are not interested in the devices under investigation, or the investigation is too burdensome for them. These may be indicated by (i) considerable difficulty in recruiting subjects to the investigation, (ii) there is an excessive amount of subjects that drop out, or (iii) the subjects indicate that they are not interested or willing to play the game for more than a few hours. In these cases, at the joint discretion of the principal and coordinating investigators, the investigation may be terminated prematurely.

3.7.5.4 Otherwise

If the investigational device is not clearly beneficial, harmful, or futile, the investigation will be continued as planned in this CIP.

3.8. Data management

3.8.1 General information

The subject data is managed responsibly, securely, and with the informed consent of the subject. The access to data is only with designated researchers. Managing the data is described in detail in Appendix 4 - Privacy notice and impact assessment.

The subject is given informed consent of their rights regarding the data, including their right to withdraw their consent. The subject rights are described in detail in Appendix 2 - Participant information and consent form.

3.8.2 Data validation

Access to the server system and to the data folder is given only to authorised personnel under password verification through two security layers. All data analysis will be performed in the custom-made data-analysis platform that keeps an audit-trail of the performed data-analysis. Data validation or data cleaning procedures are designed to assure validity and accuracy of clinical data. Data validation consists of manual reviewing during data entry and computerised edit checks and queries for identifying data values that are out of range, protocol violations, incomplete or inconsistent.

When errors in clinical data are discovered during data entry, a discrepancy is created. Discrepancies are created when information is missing or is illegible and needs further clarification. Discrepancy forms are sent to the coordinating investigator.

3.8.3 Record keeping and archiving

The study specific essential documents must be retained until at least 15 years after the completion of the study. The investigator must not destroy any study specific documentation before receiving written permission for this from the sponsor.

3.9 Amendments to the CIP

The beginning of this document includes a version history where possible amendments are made visible. The previous versions of the CIP are stored and recoverable.

3.10 Follow-up and management of deviations from the CIP at investigational sites

Bhatt (2012) differentiates deviation from violation in that deviation has less significant consequences than violation. It is possible that CIP deviation or violation occurs due to the subjects or the researchers.

3.10.1 Subjects deviations or violations

The majority of human made deviations are mitigated because the majority of the intervention is digital: answering questionnaires as well as playing the game. Wherever possible, we have mitigated the possibility for the subject to deviate from the CIP.

Before the subject is included in the research, they complete the signup process (see 3.7.1.1), first set of clinical questionnaires (see 3.7.1.2), and their MDD diagnosis is confirmed through clinical interview (see 3.7.1.5). Only then the subject is randomised to MEL-T01, MEL-S01, or TAU group, and they are given access to the intervention (for groups MEL-T01 and MEL-S01). Thus we mitigate the risk of the subject not meeting the inclusion/exclusion criteria.

When the subject arrives at T1, T2, T3, and T4, they are emailed the instructions to complete clinical questionnaires. In addition, the reminder to complete the questionnaires is shown to the MEL-T01 and MEL-S01 group in the game, and they are not able to make progress until they have completed the questionnaires. The questionnaires are filled online. If the subject doesn't fill the questionnaires in 7 days from the onset of T1, T2, T3, or T4, they are followed up with a phone call by the CSC.

The subject is recommended to play the game for 48 hours during the 12 week play period. To be included in the sample we require 24 hours of gameplay. When the subject is contacted by the CSC, the CSC has access to the subject total game time and number of weeks played (but they do not know the subject group). If the subject total game time divided by the number of weeks played is less than 2 (the minimum required), the CSC kindly discusses the topic with the subject encouraging them towards reaching 24-48 hours of playing time during the 12 week play period.

3.10.2 Research staff deviations and violations

The nature of clinical investigation is double-blinded. The information regarding the subject group is withheld from all researchers, including the CSC who are in direct interaction with the subjects as well as from the researcher conducting the experimental interview. Thus, we mitigate the risk of breaking the blind. The rest of the interactions between the subject and the researchers is avoided. If the subject contacts the researchers or coordinating investigator, the researchers are not aware of the subject group.

The CSC are trained in using MINI to ensure the inclusion and exclusion criteria are met. There are at least two CSC to ensure sufficient human resources to keep contact with the subjects.

The subjects are encouraged to report all AE and SAE to the researchers, and they have multiple channels to do so: in-game link, email, and phone calls.

After randomisation, the subjects are randomised to three groups. The groups are handled automatically to prevent mishandling samples.

3.11 Accountability

3.11.1 Control of access to the device

Access to the software is only available as long as the digital key is valid. The digital key can be activated and deactivated remotely by the researchers. Only one install is possible with one digital key. Deactivated key prevents launching the software. The researchers can deactivate the subject's key if the subject doesn't follow the researchers instructions. Access to the game requires login to the distribution channel (Steam) and login to the game client itself.

Access to the MEL-T01 and MEL-S01 software is restricted to subjects who have completed the signup pipeline, T0 questionnaires, and gone through the clinical interview by the CSC. After this, the subjects are randomised to one of the three groups.

Whether in TAU, MEL-T01, MEL-S01 group, the access to the training is 12 weeks from the beginning of the intervention. For 2 weeks after the intervention has ended, the access to the training is denied from the user, but they can access the main menu through which they can complete the questionnaire T3 (groups MEL-T01 and MEL-S01) or T4 questionnaire (TAU group).

After the two weeks are over, the access to the software is denied, and the subject can uninstall it from their device. See Table 6 for a detailed outline of the access to the device.

Table 6: Access to the device

Access to the device											
Study arms	T0 (Before playing)	T1: T0 + 4 weeks	T2: T0 + 8 weeks	T3: T0 + 12 weeks	T3 + 2 weeks	T4: T0 + 24 weeks	T4 + 2 weeks.	After T4 + 2 weeks			
MEL-T01 intervention	T0 begins after CSC confirms the subject is eligible to the study. The subject is randomised to one of the three groups.	MEL-T01 intervention				Access to menu only.	No access to the device.				
MEL-S01 intervention		MEL-S01 intervention				Access to menu only.	No access to the device.				
Treatment as usual ("TAU")		Treatment as usual				Access to MEL-T01 or MEL-S01 intervention		Access to menu only.	No access to device.		

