The subjects ($N = 800$) volunteering to participate in this investigation are diagnosed with MDD and have an on-going mental health treatment contact with a mental health professional. The subjects are recruited through Helsinki and Uudenmaan sairaanhoitopiiri (HUS) psychiatry and Varsinais-Suomen sairaanhoitopiiri (VSSHP) psychiatry as well as online.

The subjects are randomised into three arms with equal probabilities in blocks of six consecutive subjects. Subjects in the MEL-T01 and MEL-S01 arms are engaged in the intervention for 12 weeks while those in the TAU arm are on a follow-up period during these 12 weeks.

After this 12-week period, the subjects in MEL-T01 and MEL-S01 arms enter a 12-week follow-up period and the subjects in TAU arm engage with either the MEL-T01 or MEL-S01 intervention (randomised at T0 with equal probability) for 12 weeks (See Table 1 below).

The subjects are recommended to play the investigational-device game for a total of 48 hours during the 12 weeks of active intervention with a recommended weekly dose of 4 hours. A minimum of 24 hours is needed for inclusion to hypothesis testing. The subjects are limited to a daily maximum of 1.5 hours of game time.

Prior to the intervention, a clinical interview (MINI) is performed via phone to confirm the subject's MDD diagnosis. The subjects' mental health symptoms and well-being are evaluated through online questionnaires five times: before subjects are randomised into one of the three groups (T0), and then 4 (T1), 8 (T2), 12 (T3), and 24 (T4) weeks after the study has begun.

Subject population:**Criteria for inclusion:**

Eligible subjects must fulfil all of the following criteria:

1. Between 18-65 year-old
2. Suffering from major depressive disorder
3. Have an ongoing mental health treatment contact to basic healthcare, specialised healthcare, student healthcare or occupational healthcare
4. Has sufficient eyesight with or without prescription
5. Has a Windows computer with internet connection and mouse
6. Has email and phone number

Criteria for exclusion:

Subjects who fulfil any of the following criteria are excluded from the study:

1. They have threat of self-harm
2. They have addiction to digital games
3. They have psychotic disorders
4. They are pregnant or breastfeeding
5. They have impaired ability in decision making
6. They are prisoner or forensic subject
7. They have neurological disorders such as epilepsy or brain injury

Safety assessments:

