3.6.3.2 Exclusion criteria

Subjects who fulfil any of the following criteria are excluded from the study:

1. They have a threat of self-harm (evaluated by the clinical interview, see 3.6.5.2.)
2. They have an addiction to digital games (self-reported)
3. They have psychotic disorders (self-reported)
4. They are pregnant or breastfeeding (self-reported)
5. They have impaired ability in decision making (self-reported)
6. They are prisoner or forensic subject (self-reported)
7. They have neurological disorders such as epilepsy or brain injury (self-reported)

Should the subject indicate that they have suicidal thoughts, they are evaluated by the clinical subject coordinator in the clinical interview for the severity of suicidality. If the subject has a threat of harming themselves (See 3.6.5.2 for procedures), they are excluded from the study.

The criteria are also found in Appendix 1 - Rekrytointi-ilmoitus which is given to the subjects. Only subjects who do not fill the exclusion criteria are admitted to study. To further ensure that the subjects do not meet the exclusion criteria, we contact them through the phone prior to the intervention.

The exclusion criteria are compliant with the law concerning medical research in Finland (Laki lääketieteellisestä tutkimuksesta, 9.4.1994/488; 2 luku) with respect to specific protected categories of subjects:

- Elderly (2 luku, §7)
- Underaged (2 luku, 8 §)
- Those with impaired ability to make decisions (“vajaakykyinen”), (2 luku 7 §)
- Those pregnant or breastfeeding (2 luku, 9 §)
- Prisoners or forensic psychiatric subjects (2 luku, 10 §)

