3.6.3.3 Evaluation of inclusion and exclusion criteria

The subjects are presented in written form the exclusion and inclusion criteria in the recruitment phase (Appendix 1 - Recruitment notice) and in the information regarding the study (Appendix 2 - Participant information and consent form).

After the subject has signed up to the study and filled the first set of questionnaires (T0), the clinical subject coordinator (CSC) calls them via phone to confirm they meet the inclusion and do not meet the exclusion criteria (Appendix 5 - Clinical Subject Coordinator phone call). See section 3.6.5.2.

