3.14 Safety reporting

3.14.1 Safety reporting procedures and timelines

For AE and SAE definitions, see 3.3.

The subjects are given health information regarding the device in the game (see Appendix 6 - Investigator's brochure). Should the subject experience an anticipated or unanticipated AE or an SAE, or an assumed or observed device deficiency, they are able to report them through the channels below. The subjects can:

- Provide any free-form feedback in in-game questionnaires presented 28 times during the intervention, which are monitored by the CSCs.
- Report game-related issues digitally into a Jira-based system that is accessible through the in-game main menu which is monitored by the CSCs.
- Describe their concerns in both subject-initiated and pre-scheduled (weeks 0, 4, 8, 12, and 24) phone calls with the CSCs.
- Send email to CSCs by using an email address presented both in the game main menu and in the subject's informed consent form.

The CSCs actively monitor these channels on a daily basis from Monday to Friday between 9-17 o'clock. When the subject indicates an AE, SEA, or device deficiency, the event is recorded into a secure, traceable digital system.

Timelines. The summary report for AE is delivered to the coordinating investigator on a weekly basis for review. AE that merit investigations are reported immediately to the coordinating investigator. All SAE are reported immediately to the coordinating investigator both verbally as well as in written reports.

Records. Coordinating investigators keeps a full digital record of any AE, SAE, and device deficiency. The coordinating investigator is responsible for evaluating whether the AE or SAE has a causal connection with the device use. The causality is evaluated on a scale of **possible**, **probable**, and **definitive**. In addition, the AE is evaluated for its severity from **mild** effects that are easily tolerated, **moderate** where there is discomfort, and **severe** that has significant effects. All device deficiencies are evaluated for the possibility of AE and SAE.

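### Treatment-as-usual subjects first receive the game at T3 on an eligibility check made before randomisation, at least 12 weeks earlier, and no re-check is described

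*Combined protocol and SAP*

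**What the plan says.** **The check.** After sign-up and the T0 questionnaires, the clinical subject coordinator (CSC) "calls them via phone to confirm they meet the inclusion and do not meet the exclusion criteria" (3.6.3.3). Section 3.6.3.2 states: "To further ensure that the subjects do not meet the exclusion criteria, we contact them through the phone prior to the intervention". Section 3.6.5.2 likewise places the interview after enrolment and before the intervention begins. Section 3.10.1 gives the order as sign-up, questionnaires, interview, and then: "Only then the subject is randomised to MEL-T01, MEL-S01, or TAU group". It presents this sequence as what limits the risk of ineligible subjects.

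**Access.** Section 3.11.1 makes access to the software "restricted to subjects who have completed the signup pipeline, T0 questionnaires, and gone through the clinical interview by the CSC". Table 6 in that section says "T0 begins after CSC confirms the subject is eligible to the study" and opens the game to TAU from T3 without a further condition. By the synopsis, after the first 12 weeks "the subjects in TAU arm engage with either the MEL-T01 or MEL-S01 intervention (randomised at T0 with equal probability) for 12 weeks".

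**Exclusions as risk controls.** Table 2 (3.3.1.6) rates epileptic seizure as severe, lowers its likelihood from possible to rare, and lists exclusion as the only mitigation. Section 3.3.1.2 also relies on this exclusion and adds that subjects are informed of the risk. For game addiction, exclusion is one of several precautions in both places.

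**Contact before T3.** Section 3.14.1 lists "pre-scheduled (weeks 0, 4, 8, 12, and 24) phone calls with the CSCs" among the channels by which subjects can report events. Section 3.6.3.5 specifies action on suicidal ideation. Section 3.6.3.4 lets the coordinating investigator discontinue a subject whose mental health deteriorates, and ends participation after any serious adverse event (SAE).

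**The concern.** In the MEL-T01 and MEL-S01 arms, the check, randomisation and first access follow one another. In the TAU arm, 12 weeks of follow-up lie between the check and first access. When 3.10.1 describes access after the check, it names only the two device arms; the later TAU start is not addressed there or elsewhere.

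Several exclusions describe states that can change within 12 weeks: pregnancy, neurological disorder, and addiction to games or gambling (3.6.5.2 counts gambling under the game-addiction criterion). Followed as written, the plan allows a TAU subject who has come to meet one of these to be given the game for the first time. At stake is whether the risk ratings in Table 2 hold for TAU when play starts, and whether the T3–T4 TAU data come from people known to meet the criteria at first exposure.

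**Working it through.** **1. Age of the check at first TAU access.** Table 6 starts T0 after the CSC has confirmed eligibility, and T3 is T0 + 12 weeks. The check is therefore at least 12 weeks old when TAU access opens. Section 3.6.3.3 instead places the call after the T0 questionnaires. If T0 were counted from those questionnaires, the age would be 12 weeks less the gap between questionnaire and call. In both orders the check precedes randomisation.

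**2. Number allocated to the gap.** Inputs: 800 subjects to begin the study (3.7.4.1); two of every block of six to each arm (3.6.4.2).
- TAU: 800 × 2/6 = 266.7, about 267.
- TAU share of all eventual device users if everyone starts: 2/6 = 33.3%. This agrees with the plan's own 133 of 399 analysable subjects.

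**3. Allowing for attrition.** The plan assumes 50% dropout (3.7.4.1) but does not split it by arm or time. Assumption: all device-arm subjects start, and a fraction r of TAU reaches T3 and starts. The TAU share of device users is then r/(2 + r).
- r = 1: 267 people, 33.3%
- r = 0.75: 200 people, 27.3%
- r = 0.5: 133 people, 20.0%
- r = 0.25: 67 people, 11.1%

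**4. Number who newly meet a criterion.** The documents give no incidence, so this cannot be derived. As an illustration only, an assumed 12-week incidence of 0.5% to 5% gives 0.005 × 267 ≈ 1 to 0.05 × 267 ≈ 13 people, or about 1 to 7 of 133.

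**5. What each existing safeguard covers.**
- *SAE rule (3.6.3.4, 3.15.2.1)*: mandatory. It would catch a seizure or brain injury that led to hospitalisation or significant disability, if reported. It would not catch milder events.
- *Discontinuation for deterioration (3.6.3.4)*: discretionary. It partly covers psychosis and suicidality.
- *Questionnaire monitoring (3.6.3.5, 3.6.4.3)*: CSCs see suicidality replies but are blinded to other replies, including the game addiction scale and the state-of-care questionnaire.
- *Calls at weeks 4, 8 and 12 (3.14.1)*: a route for subjects to raise concerns, not described as an eligibility check. Sections 3.7.1.2 and 3.10.1 describe follow-up calls only when a questionnaire is overdue.

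New pregnancy, non-serious neurological events and game or gambling addiction are not clearly covered by any of these.

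**The case against.** The strongest reply is that these are study-entry criteria. The plan sets no maximum interval between check and exposure in any arm, and no arm is re-screened during play: a MEL-T01 subject who becomes pregnant in week 2 is not re-checked either. This stands, and it rules out a stronger claim that a reader might infer, namely that the plan requires the check immediately before exposure. The text says only that it comes before the intervention and does not say what that means for TAU. The narrower point remains: the TAU arm alone has its first access on a check at least 12 weeks old.

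Other safeguards also operate: the SAE rule, the 90-minute daily lockout, in-game health information, email, subject-initiated calls and in-game reporting. A reader might infer that TAU subjects are unprotected at T3, and the documents do not support that. Pregnancy does not appear in Table 2 and is tied in 3.6.3.2 to Finnish law on protected groups, so the risk-control argument rests mainly on epilepsy and game addiction.

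A reader might also hold that TAU players lose the week-4 and week-8 questionnaire checks that the device arms had during play. That contrast carries little weight, because apart from suicidality the CSCs cannot see those replies.

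Finally, Appendix 5 was not available. A week-12 check there cannot be ruled out, although 3.11.1 sets out the access rule and does not mention one.

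**Conclusion.** The point holds as a gap in the described procedure. The only eligibility check precedes randomisation, TAU subjects first receive the device at T3, and nothing described in between is an eligibility check. It is clearest for pregnancy, non-serious neurological events and game or gambling addiction.

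One third (267 of 800) is a ceiling on those subject to the gap. It falls to about 133, or 20% of device users, if half of TAU start and all device-arm subjects do. A reader might take one third as the share who would start play with an exclusion condition. The documents do not support that: they give no incidence, and the illustrative figures are far smaller.

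This is a matter of safety and conduct. It changes neither the sample size nor the T0–T3 primary comparison. It is worth correcting because one of the risks concerned is rated severe with exclusion as its only mitigation in Table 2, and because the correction is cheap. The conclusion is subject to Appendix 5 containing no such check.

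**What to change.** Reconcile 3.6.3.2, 3.6.3.3, 3.6.5.2, 3.10.1 and 3.11.1/Table 6 so that the plan's existing criteria are confirmed before first device access in every arm.

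- For TAU, use the week-12 CSC call listed in 3.14.1. Reconcile that call schedule with 3.7.1.2 and 3.10.1, so that it is clear whether the call is made to everyone.
- Put the same questions to all arms, because 3.6.4.3 and 3.10.2 withhold the arm from CSCs (3.6.4.1 says investigators know who is in TAU, which should be reconciled too). CSCs can see gaming time, so identical questions avoid adding a further clue but do not guarantee concealment.
- Align the order of the CSC call and T0 between 3.6.3.3 and Table 6.
- The clinical consequence of a newly met criterion is for the sponsor to decide and state.

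The cost is a few extra questions per call if the week-12 call is routine. If calls are made only for overdue questionnaires, it is one added call for each subject who reaches week 12. The exploratory T3–T4 TAU data may be slightly fewer.
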